10.1 Point of Enrollment

Subjects will be considered enrolled into the study at the time of the study-specific Informed Consent Form (ICF) execution. Subjects who have signed informed consent but do not undergo the study procedure are considered screen failures. Screen failures will be recorded

in the Electronic Data Capture (EDC) system by each study site and will not count toward total study enrollment.

In the case it is determined that the subject failed to meet the inclusion/exclusion criteria after the subject has agreed to participate in the study and has signed the informed consent, the study personnel will complete the Screening form and the End of Study form.

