19.1 Reportable Events by investigational site to Boston Scientific

It is the responsibility of the investigator to assess and report to BSC any event which occurs in any of following categories:

- All Non-Serious Adverse Events related to the Study Device and/or Study Procedure
- All Serious Adverse Events including those related to the Study Device and/or Study Procedure
- All events with a Fatal Outcome
- All Device Deficiencies
- Unanticipated Adverse Device Effects/Unanticipated Serious Adverse Device Effects
- New findings/updates in relation to already reported events

When possible, the medical diagnosis should be reported as the Event Term instead of individual symptoms.

If it is unclear whether or not an event fits one of the above categories, or if the event cannot be isolated from the device or procedure, it should be submitted as an adverse event and/or device deficiency.

Any reportable event, experienced by the study subject after informed consent, whether prior to, during or subsequent to the procedure, must be recorded in the eCRF.

Underlying diseases and chronic conditions are not reported as AEs unless there is an increase in severity or frequency during the course of the investigation. Death should not be recorded as an AE, but should only be reflected as an outcome of one (1) specific SAE (see Table 19.2-1 for AE definitions).

Refer to Instructions for Use or Investigator Brochure for the known risks associated with the device(s).

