7.3 Rules and Definitions

- Binary event rates (proportions) will be reported on a per-patient basis.
- The last follow-up date will be the latest of the following dates for each patient: date of an adverse event, procedure date, follow-up visit date, and device event date.
- Serious Adverse Event will be defined as an adverse event that:
 - Led to death
 - Led to a serious deterioration in the health of the subject that either resulted in:
 - a life-threatening illness or injury, or
 - a permanent impairment of a body structure or a body function, or

- in-patient hospitalization or prolonged hospitalization (of an existing hospitalization), or
- medical or surgical intervention to prevent life-threatening illness or injury or permanent impairment to a body structure or a body function
- o Led to fetal distress, fetal death, or a congenital abnormality or birth defect.
- When calculating rates of adverse events, missing and partial dates will be handled as follows:

Partial Date Description	Action Taken
Entire onset date is missing	The procedure date will be used for the
	onset date.
The month and the day of the month are	January 1 will be used for the month and
missing but the year is available	day of the onset date. However, if the
	imputed date falls before the procedure
	date, then the procedure date will be used
	for the onset date.
Day is missing, but the month and year are	The 1 st will be used as the day of the onset
available	date. However, if the imputed date falls
	before the procedure date, then the
	procedure date will be used for the onset
	date.

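### SAP 7.3 resets a partial onset date to the procedure date even when the known month or year shows that the event came before the procedure

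*SAP*

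**What the plan says.** SAP section 7.3 introduces its date table with "When calculating rates of adverse events, missing and partial dates will be handled as follows". The table has three rows.

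- **Onset date wholly missing:** the procedure date is used.
- **Only the year known:** the first day of that year is used (the entry begins "January 1 will be used for the month and").
- **Month and year known** (the row that begins "Day is missing, but the month and year are"): the 1st of that month is used.

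The second and third rows carry the same override for an imputed onset that is earlier than the procedure. Its operative words are "date, then the procedure date will be used". The imputed date is the only thing tested.

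The protocol allows events before the procedure to be on file. Section 10.1 states: "Subjects will be considered enrolled into the study at the time of the study-specific Informed Consent Form (ICF) execution". Section 19.1 states: "Any reportable event, experienced by the study subject after informed consent, whether prior to, during or subsequent to the procedure, must be recorded". That section also makes every serious adverse event reportable, whether related or not, but non-serious events only when related to the study device or study procedure.

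**The concern.** Moving an uncertain onset to the procedure date is a sensible default when the event could have happened on either side of the procedure. It is not sensible when the recorded month or year already excludes a later onset. In that case the rule replaces true partial information with a date known to be false.

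What is at stake is attribution in time. An event that preceded the clip could be reported as occurring on the day of the clip. The clearest exposure is an outcome with a stated time limit. Post procedural bleeding (SAP section 5.1) is limited to the 30 days after clip placement, and a bleed moved to the procedure day would fall inside that limit. Any adverse event rate that the analysts count from the procedure is exposed in the same way.

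**Working it through.** The plan states no figure on this point, so there is none to reproduce. The check applies the rule literally.

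**Inputs.** The imputation steps and the override come from SAP 7.3. The procedure date, 15 June 2023, is assumed for illustration.

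**Rule.** Let d be 1 January of the known year, or the 1st of the known month. If d is before the procedure date, the onset is the procedure date. Otherwise the onset is d.

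| Recorded onset | d | Onset under SAP 7.3 | What the known part shows | Onset if the override required a matching month or year |
|---|---|---|---|---|
| 2022 only | 1 Jan 2022 | 15 June 2023 | certainly before | stays pre-procedure |
| May 2023 | 1 May 2023 | 15 June 2023 | certainly before | stays pre-procedure |
| 2023 only | 1 Jan 2023 | 15 June 2023 | undecided | 15 June 2023 |
| June 2023 | 1 June 2023 | 15 June 2023 | undecided | 15 June 2023 |
| July 2023 | 1 July 2023 | 1 July 2023 | certainly after | 1 July 2023 |
| wholly missing | none | 15 June 2023 | undecided | 15 June 2023 |

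Only the first two rows are wrong. The rows that are truly undecided come out the same under either rule, so the conservative default is kept.

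**Can such records exist?** Yes. Recording starts at consent (Protocol 10.1 and 19.1), and neither document limits the time from consent to procedure.

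**Does anything else correct the date?** Neither document has a step that takes known pre-procedure events out of adverse event rates. SAP 7.2 says output is produced by program without manual steps, so the rule would run as written.

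**Size per subject.** SAP 7.3 reports binary rates per patient, so one wrongly counted patient adds 1/n:

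- n = 217: 1/217 = 0.46 percentage points
- n = 240: 1/240 = 0.42 percentage points

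The documents give no frequency of partial dates. If 1 to 5 patients were affected (an assumption), the shift would be:

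- n = 217: 0.46 to 2.30 points (5/217)
- n = 240: 0.42 to 2.08 points (5/240)

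Zero is also plausible. A patient who already has a qualifying event adds nothing.

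**The case against.** The strongest reply is that the exposed set is close to empty, and most of that reply stands.

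- **Few events qualify.** Unrelated non-serious events are not reportable (Protocol 19.1). What remains is mainly a serious event after consent, before the clip, in an earlier calendar month or year, with the day unknown. Serious events must be reported within 3 or 10 calendar days of awareness, depending on the study's market status (Protocol 19.4), and data are reviewed and queried (Protocol 13.1). An unknown day should be rare.
- **Emergent cases may have no window.** They can consent after the procedure (Protocol 9.1), which leaves no time between consent and procedure.
- **The schedule points the other way.** The data collection table in Protocol 11.1 marks adverse event assessment only from the procedure onward. Section 19.1 is nevertheless explicit that earlier events after consent must be recorded.
- **No window is defined.** The SAP states no general post-procedure window for adverse event rates. If a rate counted every recorded event, moving the date would change nothing. This stands, and it is why the point is confined to outcomes and rates measured from the procedure.
- **The bleeding route is not spelled out.** Neither document says that post procedural bleeding is derived from imputed onset dates. This also stands: the consequence is possible, not demonstrated.

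None of this repairs the rule. Where a qualifying record exists, the plan prescribes a false date.

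**Conclusion.** Wrong as written, minor. The defect is in a stated rule, not in missing detail. It affects few subjects, possibly none, at just under half a percentage point each. That conclusion assumes that at least one partially dated pre-procedure event is recorded and that the affected rate or outcome is counted from the procedure.

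The documents do not support three stronger readings that a reader might infer.

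- **That the rule always inflates adverse event rates.** This would need a post-procedure counting window, which the SAP does not state for general rates.
- **That the primary safety result is in doubt.** That endpoint counts only serious events related to the clip or the study portion of the procedure. Lack of a temporal relationship is a ground for judging an event not related (Protocol 19.3), and nothing says the imputed date feeds that judgement. One narrow route remains: an event whose relatedness cannot be assessed is classed as possibly related. Even then the count goes up, which works against the device and cannot produce a false pass.
- **That the share of subjects whose consent and procedure fall in different calendar months measures the problem.** It does not. Such a subject must also have a reportable event in the earlier month with the day missing, and the documents give neither the interval nor the frequency.

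**What to change.** Add one condition to both partial-date rows of SAP 7.3: use the procedure date only when the known month and year (or the known year, if that is all there is) equal those of the procedure. When the known part is earlier, keep the onset as pre-procedure.

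Add a sentence that partially and fully dated pre-procedure events are handled alike: listed, but not counted in rates or outcomes measured from the procedure. Without it, the amended rows would exclude partially dated events while the SAP stayed silent on fully dated ones.

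The cost is a sentence or two in the SAP and one condition in the program. SAP 5.9 provides the route: an amended SAP approved before the analyses are run. No data collection or sample size changes.
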